Document Coversheet

Study Title: Creating Harmony at HOME: A Pilot Study of a Telehealth Based Program for Rural Caregivers' Ability to Adapt Home Environments for Adults With ADRD

Institution/Site:	University of Kentucky
Document (Approval/Update) Date:	Protocol 7/17/23
NCT Number:	NCT05202223
IRB Number	66766
Coversheet created:	10/30/23

NCT05202223: Creating Harmony at HOME: A Pilot Study of a Telehealth Based Program for Rural Caregivers' Ability to Adapt Home Environments for Adults With ADRD

Statistical analysis plan:

Analysis included mean and standard deviation of each endpoint at each visit. A linear mixed model was completed to determine if the mean response varied among the 3 visits (P value listed in the last column). Final analyses used a modified intent to treat (mITT) for a completers analysis which included those participants who completed visit 2.

-Which IRB-

Medical
 OnMedical

-Protocol Process Type-

Exemption

IMPORTANT NOTE: You will not be able to change your selections for "Which IRB" and "Protocol Process Type" after saving this section. If you select the wrong IRB or Protocol Process Type, you may need to create a new application.

See below for guidance on these options, or refer to ORI's "Getting Started" page. Please contact the Office of Research Integrity (ORI) at [contact] with any questions prior to saving your selections.

Which IRB

The Medical IRB reviews research from the Colleges of:

- Dentistry
- Health Sciences
- Medicine
- Nursing
- Pharmacy and Health Sciences
- and Public Health.

The Nonmedical IRB reviews research from the Colleges of:

- Agriculture
- Arts and Sciences
- Business and Economics
- Communication and Information
- Design; Education
- Fine Arts
- Law
- and Social Work

Note: Studies that involve administration of drugs, testing safety or effectiveness of medical devices, or invasive medical procedures must be reviewed by the **Medical IRB** regardless of the college from which the application originates.

Which Protocol Process Type

Under federal regulations, the IRB can process an application to conduct research involving human subjects in one of three ways:

- by exemption certification
- · by expedited review.
- by full review;

The investigator makes the preliminary determination of the type of review for which a study is eligible. Please refer to ORI's "Getting Started" page for more information about which activities are eligible for each type of review.

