Visit 2: Baseline data will be collected at Visit 2 consisting of seven surveys/questionnaires completed during the visit with the study coordinator: the Revised Memory and Behavior Problem Checklist, Adult Sensory Profile, Canadian Occupational Performance Measure, 6-Item Revised Caregiver Appraisal Scale; 6-Item Activities of Daily Living; 8-Item Instrumental Activities of Daily Living, Pearlin Mastery assessment, Stait-Trail Anxiety Scale, and Perceived Stress Scale. . The Situational Assessment Activity and Function Profile will be emailed or mailed to you for completion, as well. A focus group will also be held with selected participants. All intervention materials will be mailed to the patient's home following visit 2. Intervention materials will include items which offer environmental modifications to the home, for example:

Visit 3: The Occupational Therapist will meet with you for Visit 3. This will initiate week 1 in the behavior workbook. During this visit, the therapist will complete the Canadian Occupational Performance Measure, the Home Occupational Environment Assessment, and the Situational Assessment of the Home Environment.

Visit 4-8: At the end of each week, you and the patient you care for will meet with an occupational therapist to complete intervention training, as well as review the behavior journal and adverse events. These visits will last approximately one hour.

Visit 9: At the final week of intervention, you will engage in a two-hour session which will involve of adverse events, and completion of the Revised Memory and Behavior Problem Checklist, CES Depression scale; 6-Item Revised Caregiver Appraisal Scale; 6-Item Activities of Daily Living; 8-Item Instrumental Activities of Daily Living; Canadian Occupational Performance Measure, Stait-Trait Anxiety Scale; Zarit Caregiver Burden Scale, Pearlin Mastery assessment and Perceived Stress Scale surveys/questionnaires. A focus group will also be held with selected participants. The focus group will consist of the first ten participants willing to participate. The focus group will last approximately 60 minutes and will be conducted over zoom. The focus group will provide feedback needed to refine the intervention to specific needs of caregivers in rural Appalachia.

Visit 10: Four weeks following completion of the intervention, you will complete a follow up session consisting of the same visit 9 assessments.

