This study will utilize a one-arm, pre/post design. Consent will be obtained electronically using REDCap survey distribution. Researchers will assess the feasibility of the primary outcome: increased caregiver competence (Pearlin mastery sub-scale on caregiver competence). Forty persons with dementia and their caregivers will be recruited for participation from the University of Kentucky Alzheimer's Disease Center (UK-ADRC), UK Telehealth Neurology Clinic, and Kentucky Neuroscience Institute. A sample of 40 caregivers has 80% power to show that the compliance (protocol adherence) rate is =60% versus the alternative that the compliance rate is <60% at the 0.05 level of significance. This sample size will allow for assessment of feasibility as the primary outcome based on retention of =75% of study participants completing the study, with =60% protocol adherence, estimated from current clinical trials at UK-ADRC and rehabilitation feasibility trials. All data will be collected remotely and stored electronically on REDCap servers approved by the University of Kentucky IRB. Statistical analyses will be completed using R and SAS programming Exploratory analyses will be conducted to gather feasibility data on the potential efficacy of with assistance from D the intervention on secondary outcomes, including behavior, functional performance, and caregiver burden, with change from baseline to the end of the study and 1-month post-intervention follow up using analysis of covariance (ANCOVA) that will include prespecified covariates (i.e., age, gender, education, disease state, comorbidities). Frequencies of demographic variables (sex, age, cognitive status, education, caregiver relationship, caregiver age), behavior change, and adverse events will be compared among participants within the same group and between groups for differences using either Fisher Exact or chi-square tests.

[figure not shown]
Intervention description:

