Perceived Stress Scale: Scale to assess caregiver stress.

6-Item Revised Caregiver Appraisal Scale: Assessment of caregiver satisfaction related to intervention.

Revised Memory and Behavior Problems Checklist: Caregiver report of behavioral concerns presented by the patient.

Situational Assessment- Activity and Function Profile: Caregiver report of situational elements and patient participation of activities completed within the home.

Situational Assessment of the Home Environment: Therapist led review of home environment accessibility and set up for patient use. Stait-Trait Anxiety Scale: Assessment of caregiver-reported feelings of anxiety.

UCLA Loneliness Scale: Assessment of caregiver-reported feelings of loneliness.

Zarit Caregiver Burden Scale: A brief assessment of caregiver burden associated with patient care, to be completed by the caregiver. Will be mailed or emailed to the caregiver.

Focus groups of the first ten participants who are willing to participate will engage in an online Zoom focus group pre intervention and post intervention with goals to culturally adapt the intervention for those living in Appalachia, and to gain feedback regarding their experience with the intervention.

Feasibility as measured by caregiver competence will be assessed as the primary outcome of this study. Primary outcome: Caregiver mastery will be assessed using the 4-item Pearlin mastery sub-scale on caregiver competence (a=.74) at pre- and post-test and one-month post-intervention follow up. Exploratory outcomes will examine impact of the intervention on caregiver burden (4 item Zarit Burden Interview; a=.78), stress (10-item Perceived Stress Scale; a=.84-.86), the 6-item caregiver appraisal sub-scale on caregiver satisfaction a=.67-.76), and change in BPSD (24-item Revised Memory and Behavior Problems Checklist; a=.67-.90) at pre- and post-test. These measures are included in the attachment.

Attachments

Attachments	
Attach Type	File Name
DataCollection	Focus Group 1 Interview Guide_rev.docx
DataCollection	Focus Group 1 Interview Guide_v2 clean.docx
DataCollection	Focus Group 2 Post Interview Guide_rev.docx
DataCollection	Focus Group 2 Post Interview Guide_v2 Clean.docx
DataCollection	HARMONY AT HOME PARTICIPANT MANUAL 1-16-22.pdf
DataCollection	SAAF.pdf
DataCollection	HARMONY AT HOME PARTICIPANT WORKBOOK highlighted 1-19-22.docx
DataCollection	HARMONY AT HOME PARTICIPANT MANUAL 1-16-22.docx
DataCollection	SAAF revised highlighted 1-19-22.docx

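### The outcome paragraph omits the one-month visit for the exploratory outcomes, and the SAP's only test, an omnibus P value over three unnamed visits, cannot show whether a post-test gain lasted

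*Combined protocol and SAP*

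**What the plan says.** Four places in the combined document bear on when the exploratory outcomes are assessed.

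- **Data Collection & Research Materials, outcome paragraph.** Caregiver mastery, the primary outcome, is assessed "at pre- and post-test and one-month post-intervention follow up". The next sentence lists the exploratory outcomes: burden, stress, caregiver satisfaction and, last, "change in BPSD (24-item Revised Memory and Behavior Problems Checklist; a=.67-.90) at pre- and post-test". The one-month visit is not mentioned for them.
- **Research Procedures, statistical paragraph.** ANCOVA is planned for "secondary outcomes, including behavior, functional performance, and caregiver burden, with change from baseline to the end of the study and 1-month post-intervention follow up".
- **Research Procedures, Visits 9 and 10.** Visit 9 includes "completion of the Revised Memory and Behavior Problem Checklist, CES Depression scale; 6-Item Revised Caregiver Appraisal Scale", and further along the same list the Zarit and Perceived Stress scales. For Visit 10: "Four weeks following completion of the intervention, you will complete a follow up session consisting of the same visit 9 assessments".
- **Statistical analysis plan (coversheet).** Means and standard deviations are given for each endpoint at each visit, and "A linear mixed model was completed to determine if the mean response varied among the 3 visits". The three visits are not identified.

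**The concern.** Read together, these places do not say whether the one-month data belong to the stated assessment of the exploratory outcomes. The sentence just before names the one-month visit for mastery, so the shorter wording is hard to read as shorthand for all three time points.

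What is at stake is how a gain that fades should be read. Weekly therapist contact ends at Visit 9. A change present at Visit 9 and gone at Visit 10 means something different from one that persists, and the pilot is meant to inform the next phase of intervention development. The plan collects the data needed to tell these apart, but specifies no inferential result that does so.

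**Working it through.** **Step 1: the time points side by side**

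| Place | Outcomes covered | Time points |
|---|---|---|
| Outcome paragraph | burden, stress, satisfaction, BPSD | pre, post |
| Statistical paragraph | behavior, function and burden named; the list is open-ended | study end, one month |
| Visits 9 and 10 | all four, through their scales | post, one month |
| SAP | each endpoint | three visits, not named |

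Only the visit schedule expressly covers all four outcomes at one month. Stress and satisfaction enter the statistical paragraph only through its open-ended list.

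The SAP's three visits fit baseline, Visit 9 and Visit 10. The behavior checklist, Perceived Stress Scale and Caregiver Appraisal Scale are listed at Visit 2, Visit 9 and Visit 10 and nowhere else. The Zarit scale is not in the Visit 2 list. Its first administration is in the survey sent out at the screening visit (Visit 1), so its baseline comes from a different visit. This reading of the SAP is an inference, though it is the one that fits the schedule.

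**Step 2: what the omnibus test can show**

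The documents give no effect size, standard deviation or correlation for these outcomes. Their one power figure, 80% with 40 caregivers, concerns protocol adherence and does not bear on this. The following inputs are therefore assumptions, apart from n:

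- n = 30, which is the 75% retention target applied to 40 caregivers.
- Post-test gain d = 0.4 SD.
- Equal variances and equal correlation rho = 0.5 to 0.7 between any two visits.
- Two-sided 0.05, with a repeated-measures F test on 2 and 2(n−1) = 58 degrees of freedom standing in for the mixed model.

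The noncentrality is λ = n × S / (1 − rho), where S is the sum of squared deviations of the three visit means from their average.

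- Gain fully kept, means (0, d, d): S = (4/9 + 1/9 + 1/9)d² = (2/3)d².
- Gain fully lost, means (0, d, 0): S = (1/9 + 4/9 + 1/9)d² = (2/3)d².
- Half kept, means (0, d, d/2): S = (1/4 + 1/4 + 0)d² = (1/2)d².

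Kept and lost give the same S, hence the same λ and the same power for any d, n and common rho. With d = 0.4, (2/3)d² = 0.1067 and (1/2)d² = 0.08:

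- Kept or lost: λ = 30 × 0.1067 / 0.5 = 6.4 and 30 × 0.1067 / 0.3 = 10.67.
- Half kept: λ = 30 × 0.08 / 0.5 = 4.8 and 30 × 0.08 / 0.3 = 8.0.

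From the noncentral F (critical value 3.16), and from paired t tests with noncentrality (mean change) × √n / √(2(1 − rho)):

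| At one month | Omnibus, 3 visits | Visit 9 − baseline | Visit 10 − baseline |
|---|---|---|---|
| fully kept | 59% to 82% | 56% to 78% | 56% to 78% |
| half kept | 47% to 69% | 56% to 78% | 19% to 28% |
| fully lost | 59% to 82% | 56% to 78% | 5% |

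The omnibus column has the same entry in its first and last rows. The Visit 10 column separates them.

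**Step 3: check by simulation**

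With 20,000 simulated trials per setting, d = 0.5 SD, n = 30 or 40 and the same correlations, the omnibus test was significant in 79% to 99% of trials when the gain was kept and 80% to 99% when it was lost. The chance that Visit 9 was significant while Visit 10 was not ran from 2% to 13% if kept and from 72% to 93% if lost.

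**The case against.** The strongest reply is that the outcome paragraph is a lone outlier in a section about data collection. It specifies no test and excludes no data. The other places point to three time points, and the SAP's means by visit would let a reader see fading. All of this stands. The closing words could also be read as attaching only to BPSD, the last item in the sentence. A caregiver schedule of events is listed among the attachments but was not available, and it may settle the matter.

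A reader might infer something stronger: that the document contains two rival analyses, so that the same endpoint could be declared improved or not sustained according to the passage followed. The documents do not support that. No success rule exists for these outcomes, the outcome paragraph names no analysis, and the choice between ANCOVA in the protocol and a mixed model in the SAP is a separate matter.

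A reader might also infer that the inconsistency costs power. It does not. The low power of the Visit 10 contrast under fading follows from assuming a smaller effect there. The omnibus test loses about 9 points against the Visit 9 contrast only when half the effect remains; when the gain is fully kept or fully lost, it is slightly above that contrast.

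Lastly, the statistical paragraph's mention of study end beside a separate one-month follow-up most naturally means the end of the intervention. That is loose wording, since Visit 10 is the last listed visit, but not a second contradiction.

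What remains is that descriptive means carry no measure of uncertainty for the change within participants, and the single P value gives neither direction nor timing.

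**Conclusion.** The inconsistency is real but limited. The outcome paragraph omits a time point that the visit schedule collects for all four exploratory outcomes, that the statistical paragraph analyses for secondary outcomes, and that the SAP very probably includes among its three visits.

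The consequence is one of interpretation. The SAP's only inferential result is as likely to be significant for a gain that is fully lost at one month as for one fully kept: about 59% to 82% in both cases under the stated assumptions. The percentages depend on the assumed 0.4 SD, correlations and n. The equality does not depend on the size of the gain or on n, but it does require equal variances and equal correlations across visits.

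These are exploratory outcomes in a one-arm feasibility pilot. The primary outcome, the sample size and data collection are not affected.

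**What to change.** 1. **Outcome paragraph:** state baseline, post-test (Visit 9) and one-month follow-up (Visit 10) for the exploratory outcomes.
2. **Statistical paragraph:** replace the reference to study end with post-test (Visit 9).
3. **SAP:** name the three visits using the protocol's numbering, and note that the Zarit baseline is taken at screening.
4. **SAP:** from the same mixed model, report Visit 9 minus baseline and Visit 10 minus baseline with 95% confidence intervals for each outcome, labelled exploratory.

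The intervals should carry the interpretation, because a non-significant Visit 10 contrast does not show that a gain was lost. At n = 30 the half-width is about 2.045 × √(2(1 − rho)/30), which is 0.37 SD at rho = 0.5 and 0.29 SD at rho = 0.7.

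The cost is wording in two protocol paragraphs and a few lines in the SAP, with no added visits, measures or participants. The SAP is written in the past tense and the record is marked closed. If the analysis is already complete, the contrasts can be reported from the existing data as a clarification, rather than by rewriting the protocol after the fact.

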1.0 PARTICPANTS SAFETY

1.1 Potential Risks and Benefits for Participants

Potential Risks:

This study poses minimal risk. There is minimal risk associated with potential breach of privacy and confidentiality. There is possible stress linked to carrying out the environmental modifications in addition to regular caregiving activities and possible emotional distress associated with research interviews. Some of the modifications to the sensory environment may include the use of topical lotions. It is minimally possible that these may cause skin irritation, rash, or dermatitis.

Potential Benefits:

It is unknown if this study will create notable benefits. However, some individuals have experienced improved relationships with those they care for, and empowered decision making while caregiving. Patients may experience relaxed moods with decreased occurrence of behavioral disruption when participating in activities included in this study.

1.2 Adverse Event and Serious Adverse Event Collection and Reporting

The only expected possibly deleterious outcomes for informal caregiver participants are minor and transient emotional upset experienced while participating in program modules, research surveys and interviews, as well as possible breach of confidentiality. The other possible deleterious outcomes for the caregiver are those related to minor skin irritation.

1.2.1 Adverse Event (AE):

Any untoward or unfavorable medical occurrence in a human study participant, including any abnormal sign (e.g. abnormal physical exam or laboratory finding), symptom, or disease, temporally associated with the participant's involvement in the research, whether or not considered related to participation in the research. As noted above, the only expected AEs with possibly deleterious outcomes for this study are risks of minor and transient emotional upset experienced while participating in program modules, research surveys and interviews, as well as possible breach of confidentiality. The other possible deleterious outcomes for the caregiver are those related to minor skin irritation.

1.2.2 Serious Adverse Event (SAE):

Any adverse event that:

Results in death

Is life threatening, or places the participant at immediate risk of death from the event


24 hours of notification; the PI will also inform the IRB of any such events within the time frame specified by the IRB. Beginning with the initiation of the intervention study activities, the PI (())) will be responsible for providing quarterly summary reports of SAEs to the NIA Program Officer and the SO. Beginning with the

initiation of intervention study activities, safety reports will be sent to the SO twice a year and will include a detailed analysis of study progress, data and safety issues. Such reports will be developed by the PI and Co-I but reviewed by key study personnel and, as

66767 **CLOSED** appropriate, study consultants and advisors. 3.2 Data Analysis and Coordination All quantitative data will be stored in a REDCap database. Data from individual subjects will be deidentified and stored using ID numbers; the document linking subject names and ID numbers will not be part of that database but will be stored in secure server at Sanders-Brown Center on Aging in a password-protected file. Qualitative data transcripts will be de-identified and also stored on this server in password-protected files. Transmission of de-identified study data will occur over secure emails messages. Data management and analysis will be conducted by PhD, project CO-I. Study participants will receive a 1 to 2 page summary of study results either by mail or email, depending on the preference, prior to destroying participant contact information. 3.3 Content of Data and Safety Monitoring Report) will provide semi-annual data safety and monitoring reports to the NIA Program Officer and the SO. Each report The study PI will update the previous report. Each report will summarize: Overall study status Study participant characteristics Study recruitment and retention statistics Data completeness Summary statistics on caregiver and care recipient outcome measures Deployment of the risk protocol based on observations or scale scores Unanticipated Serious Adverse Events, including Deaths. 3.4 DSMB Membership and Affiliation The Safety Officer for this study will be: College of Medicine University of Kentucky is a seasoned physician with extensive knowledge of clinical trial, as well as clinical research involving stroke and epilepsy, similar to dementia research. Through the UK College of Medicine, she has at her disposal a variety of methodological and statistical experts, should she need them to fulfill my responsibilities as Safety Officer. 3.5 Conflict of Interest for DSMB/SO has no direct involvement with the current study; her biosketch indicating that she has no conflict of interest is attached. 3.6 Protection of Confidentiality Data will be presented in a de-identified manner in SO reports. In meetings with the SO, data and discussion are confidential. Participant identities will not be known to the SO. 3.7 DSMB/SO Responsibilities The SO will: Review the research protocol, informed consent documents and plans for data safety and monitoring; Recommend subject recruitment be initiated after receipt of a satisfactory protocol; Evaluate the progress of the trial, including periodic assessments of data quality and timeliness, recruitment, accrual and retention, participant risk versus benefit, performance of the trial sites, and other factors that can affect study outcome; Consider factors external to the study when relevant information becomes available, such as scientific or therapeutic developments that may have an impact on the safety of the participants or the ethics of the trial; Review study performance, make recommendations and assist in the resolution of problems reported by the Principal Investigator; Protect the safety of the study participants; Report to NIA on the safety and progress of the trial; Make recommendations to the NIA and the Principal Investigator concerning continuation, termination or other modifications of the trial based on the observed beneficial or adverse effects of the treatment under study; If appropriate, review interim analyses in accordance with stopping rules, which are clearly defined in advance of data analysis and have the approval of the SO; Ensure the confidentiality of the study data and the results of monitoring; and, Assist the NIA by commenting on any problems with study conduct, enrollment, sample size, and/or data collection. Back to Top Future Use and Sharing of Material (e.g., Data/Specimens/Information)

Future Use and Sharing of Material (e.g., Data/Specimens/Information)

If the material collected for this study will be used by members of the research team or shared with other researchers for future studies, please address the following:

- list the biological specimens and/or information that will be kept
- · briefly describe the types, categories and/or purposes of the future research
- · describe any risks of the additional use
- describe privacy/confidentiality protections that will be put into place
- describe the period of time specimens/information may be used
- describe procedures for sharing specimens/information with secondary researchers
- describe the process for, and limitations to, withdrawal of specimens/data

N/A

Are you recruiting or expect to enroll Non-English Speaking Subjects or Subjects from a Foreign Culture? (does not include short form use for incidentally encountered non-English subjects)

66767 CLOSED

⊂ Yes 🤉 No

-Non-English Speaking Subjects or Subjects from a Foreign Culture

Recruitment and Consent:

Describe how information about the study will be communicated to potential subjects appropriate for their culture, and if necessary, how new information about the research may be relayed to subjects during the study. When recruiting Non-English-speaking subjects, provide a consent document in the subject's primary language. After saving this section, attach both the English and translated consent documents in the "Informed Consent" section.

Cultural and Language Consultants:

The PI is required to identify someone who is willing to serve as the cultural consultant to the IRB.

- This person should be familiar with the culture of the subject population and/or be able to verify that translated documents are the equivalent of the English version of documents submitted.
- The consultant should not be involved with the study or have any interest in its IRB approval.
- Please include the name, address, telephone number, and email of the person who agrees to be the cultural consultant for your study.
- ORI staff will facilitate the review process with your consultant. Please do not ask them to review your protocol separately.

For more details, see the IRB Application Instructions on Research Involving Non-English Speaking Subjects or Subjects from a Foreign Culture.

Local Requirements:

If you will conduct research at an international location, identify and describe:

- relevant local regulations
- data privacy regulations
- applicable laws
- · ethics review requirements for human subject protection

Please provide links or sources where possible. If the project has been or will be reviewed by a local ethics review board, attach a copy in the "Additional Information/Materials" section. You may also consult the current edition of the International Compilation of Human Research Standards

Does your study involve HIV/AIDS research and/or screening for other reportable diseases (e.g., Hepatitis

HIV/AIDS Research—

If you have questions about what constitutes a reportable disease and/or condition in the state of Kentucky, see ORI's summary sheet: "Reporting Requirements for Diseases and Conditions in Kentucky" [PDF].

HIV/AIDS Research: There are additional IRB requirements for designing and implementing the research and for obtaining informed consent. Describe additional safeguards to minimize risk to subjects in the space provided below.

For additional information, visit the online IRB Survival Handbook to download a copy of the "Medical IRB's requirements for Protection of Human Subjects in Research Involving HIV Testing" [D65.0000] [PDF], and visit the Office for Human Research Protections web site for statements on AIDS research, or contact the Office of Research Integrity at [contact].

PI-Sponsored FDA-Regulated Research

Is this an investigator-initiated study that:

1) involves testing a Nonsignificant Risk (NSR) Device, or

2) is being conducted under an investigator-held Investigational New Drug (IND) or Investigational Device Exemption (IDE)? c Yes c No

PI-Sponsored FDA-Regulated Research

If the answer above is yes, then the investigator assumes the regulatory responsibilities of both the investigator and sponsor. The Office of Research Integrity provides a summary list of sponsor IND regulatory requirements for drug trials [PDF], IDE regulatory requirements for SR device trials [PDF], and abbreviated regulatory requirements for NSR device trials [PDF]. For detailed descriptions see FDA Responsibilities for Device Study Sponsors or FDA Responsibilities for IND Drug Study Sponsor-Investigators.

- Describe the experience/knowledge/training (if any) of the investigator serving as a sponsor (e.g., previously held an IND/IDE); and
- Indicate if any sponsor obligations have been transferred to a commercial sponsor, contract research organization (CRO), contract monitor, or other entity (provide details or attach FDA 1571).

IRB policy requires mandatory training for all investigators who are also FDA-regulated sponsors (see Sponsor-Investigator FAQs). A sponsor-investigator must complete the applicable Office of Research Integrity web based training, (drug or device) before final IRB approval is granted.

Has the sponsor-investigator completed the mandatory PI-sponsor training prior to this submission? • Yes • No

If the sponsor-investigator has completed equivalent sponsor-investigator training, submit documentation of the content for the IRB's consideration.

Attachments

0 unresolved comment(s)

(Visit ORI's Health Insurance Portability and Accountability Act (HIPAA) web page to determine if your research falls under the HIPAA Privacy Regulation.)

If yes, check below all that apply and attach the applicable document(s): 🔮

□ HIPAA De-identification Certification Form
 □ HIPAA Waiver of Authorization
 Attachments
 Attach Type File Name
 Waiver
 WoA Approval Letter - IRB# 66767.pdf
 Waiver
 Wor K 6-24.pdf

0 unresolved comment(s)

The term drug may include:

- FDA approved drugs,
- unapproved use of approved drugs,
- investigational drugs or biologics,
- other compounds or products intended to affect structure or function of the body, and/or
- complementary and alternative medicine products such as dietary supplements, substances generally recognized as safe (GRAS) when used to diagnose, cure mitigate, treat or prevent disease, or clinical studies of e-cigarettes examining a potential therapeutic purpose.

Does this protocol involve a drug including an FDA approved drug; unapproved use of an FDA approved drug; and/or an investigational drug?

○ Yes ⊂ No

If yes, complete the questions below. Additional study drug guidance.

Drug Name:	
Non-Oncology). Use of IDS is	quired by Hospital Policy to utilize Investigational Drug Service (IDS) pharmacies (Oncolog s highly recommended, but optional for outpatient studies. Outpatient studies not using IDS lic inspection by the IDS for compliance with drug accountability good clinical practices.
ndicate where study drug(s)	will be housed and managed:
Investigational Drug Se	ervice (IDS) UK Hospital
Other Location:	
r Yes r No If Yes, list IND #(s) and	complete the following:
IND Submitted/Held by:	
IND Submitted/Held by: Sponsor: ℾ	Held By:
Sponsor: 🗖	Held By:
Sponsor: ⊏ Investigator: ⊏ Other: ⊏ ⊂ Checkmark if the stu or if this is an Individua	Held By: Held By: Held By: Held By: dy is being conducted under FDA's Expanded Access Program (e.g., Treatment IND) I Patient Expanded Access IND (FDA Form 3926).
Sponsor: ⊏ Investigator: ⊏ Other: ⊏ ⊂ Checkmark if the stu or if this is an Individua	Held By: Held By: Held By: Held By: dy is being conducted under FDA's Expanded Access Program (e.g., Treatment IND)
Sponsor: ■ Investigator: ■ Other: ■ ■ Checkmark if the stu or if this is an Individua FDA's Expanded Acce following: • FDA Form 3926;	Held By: Held By:
Sponsor: ■ Investigator: ■ Other: ■ ■ Checkmark if the stu or if this is an Individua FDA's Expanded Acce following: ● FDA Form 3926; ● FDA expanded acc	Held By: Held By: Held By: Held By: dy is being conducted under FDA's Expanded Access Program (e.g., Treatment IND) I Patient Expanded Access IND (FDA Form 3926).
Sponsor: ■ Investigator: ■ Other: ■ ■ Checkmark if the stu or if this is an Individua FDA's Expanded Acce following: ● FDA Form 3926; ● FDA expanded acce ● Confirmation of acce	Held By:
Sponsor: ■ Investigator: ■ Other: ■ ■ Checkmark if the stu or if this is an Individua FDA's Expanded Acce following: ● FDA Form 3926; ● FDA expanded acce ● Confirmation of acce	Held By:

Attachmente	applicable drug documentation (e.g., Investigator Brochure; approved labeling; publication; FDA c etc.) should be attached using "Other Drug Documentation" for the document type.	66767 CLOSED

A DEVICE may be a:

- component, part, accessory;
- · assay, reagent, or in-vitro diagnostic device;
- software, digital health, or mobile medical app;
- other instrument if intended to affect the structure or function of the body, diagnose, cure, mitigate, treat or prevent disease; or
- a homemade device developed by an investigator or other non-commercial entity and not approved for marketing by FDA.

For additional information, helpful resources, and definitions, see ORI's Use of Any Device Being Tested in Research web page.

Does this protocol involve testing (collecting safety or efficacy data) of a medical device including an FDA approved device, unapproved use of an approved device, humanitarian use device, and/or an investigational device?

⊂ Yes ∈ No

[Note: If a marketed device(s) is only being used to elicit or measure a physiologic response or clinical outcome, AND, NO data will be collected on or about the device itself, you may answer "no" above, save and exit this section, (Examples: a chemo drug study uses an MRI to measure tumor growth but does NOT assess how effective the MRI is at making the measurement; an exercise study uses a heart monitor to measure athletic performance but no safety or efficacy information will be collected about the device itself, nor will the data collected be used for comparative purposes against any other similar device).]

If you answered yes above, please complete the following questions.

evice Name:		
the study being conducted	under a valid Investigational Device Exemption (IDE),	
umanitarian Device Exempt	on (HDE) or Compassionate Use?	
€Yes €No		
If Yes, complete the follo	wing:	
IDE or HDE #(s)		
IDE/HDE Submitted/Hel	l by:	
Sponsor: 🗖	Held By:	
Investigator: 🗖	Held By:	
Other: 🗖	Held By:	
Check if this is a Tre Expanded Access pro	eatment IDE or Compassionate Use under the Food and Drug A gram.	Administration (FDA)
For Individual or Small and attach the following	Group Expanded Access, see FDA's Early Expanded Access F	Program Information,
	ess approval or sponsor's authorization;	
	sessment from an uninvolved physician, if available; eement from manufacturer or entity authorized to provide acce	ss to the product.
For guidance and repor	ing requirements at the conclusion of treatment see the Medica	al Device SOP.

Does the intended use of any research device being tested (not clinically observed) in this study meet the regul Significant Risk (SR) device?

• Yes. Device(s) as used in this study presents a potential for serious risk to the health, safety, or welfare of a subject and (1) is intended as an implant; or (2) is used in supporting or sustaining human life; or (3) is of substantial importance in diagnosing, curing, mitigating or treating disease, or otherwise prevents impairment of human health; or (4) otherwise presents a potential for serious risk to the health, safety, or welfare of a subject.

• No. All devices, as used in this study do not present a potential for serious risk to the health, safety, or welfare of subjects/participants.

Complete and attach the required Study Device Form, picking the "Study Device Form" for the document type. Any applicable device documentation (e.g., Manufacturer information; patient information packet; approved labeling; FDA correspondence, etc.) should be attached using "Other Device Documentation" for the document type.

RESEARCH SITES

0 unresolved comment(s)

To complete this section, ensure the responses are accurate then click "SAVE".

A) Check all the applicable sites listed below at which the research will be conducted. If none apply, you do not need to check any boxes.

UK Sites

- □ UK Classroom(s)/Lab(s)
- UK Clinics in Lexington
- □ UK Clinics outside of Lexington
- □ UK Healthcare Good Samaritan Hospital
- □ UK Hospital

-Schools/Education Institutions-

□ Fayette Co. School Systems *

- □ Other State/Regional School Systems
- □ Institutions of Higher Education (other than UK)

*Fayette Co. School systems, as well as other non-UK sites, have additional requirements that must be addressed. See ORI's IRB Application Instructions - Off-site Research web page for details.

-Other Medical Facilities-

- E Bluegrass Regional Mental Health Retardation Board
- Cardinal Hill Hospital
- □ Eastern State Hospital
- Norton Healthcare
- □ Nursing Homes
- Shriner's Children's Hospital
- Veterans Affairs Medical Center
- Conter Hospitals and Med. Centers
- Correctional Facilities
- □ Home Health Agencies
- □ International Sites

Research activities conducted at performance sites that are not owned or operated by the University of Kentucky, at sites that are geographically separate from UK, or at sites that do not fall under the UK IRB's authority, are subject to special procedures for coordination of research review. Additional information is required (see IRB Application Instructions - Off-Site Research web page), including:

- A letter of support and local context is required from non-UK sites. See *Letters of Support and Local Context* on the IRB Application Instructions Off-Site Research web page for more information.
- Supportive documentation, including letters of support, can be attached below.
